3.3. Rollover to Extension Study

Consenting patients that meet the A536-06 eligibility criteria may immediately roll over from A536-04 to study A536-06 following the last ACE-536 dose. These patients may forego the End of Study (EOS) visit in study A536-04 to begin study A536-06.

Patients who complete the EOS visit for study A536-04 and are \geq 28 days post EOS visit may also roll over to study A536-06. These patients will be re-assessed for eligibility by meeting all eligibility criteria plus additional inclusion criteria for study A536-06.

Patients who do not meet the above criteria (e.g., $>$ 35 days after last dose in study A536-04 and $<$ 28 days post EOS visit in study A536-04) may still participate, but should not begin study A536-06 C1D1 until they have reached \geq 28 days post EOS visit from study A536-04.

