4.1. Intent-to-Treat (ITT) Population

The intent-to-treat (ITT) population will consist of all enrolled patients. This population will be used for all efficacy analysis.

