5.6.2. RBC Transfusions

The complete RBC transfusion records prior to and during treatment will be listed for each patient. The hemoglobin values prior to transfusion will also be listed.

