5.7. Efficacy Analyses

All efficacy endpoint will be performed using the ITT population.

All efficacy summaries will be presented by dose cohort and for NTD and TD patients separately. In addition, the dose cohorts will be combined and presented as low dose group and high dose group. Low dose group includes patients on 0.2 and 0.4 mg/kg dose cohorts. High dose group includes patients on 0.6 mg/kg and above. No formal hypothesis testing is planned.

In general, below rules apply to the derivations of efficacy endpoints which utilize hemoglobin and RBC transfusion data unless specified otherwise:

- Hemoglobin measurements within 14 days following RBC transfusion will be excluded from efficacy analysis
- For each patient, all efficacy endpoints will be derived based on an analysis cut-off day, defined as the last dose + 56 days or the last date from transfusion record data, whichever is earlier.

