5.7.1. Primary Efficacy Endpoint

The primary efficacy endpoint is the proportion of β -thalassemia patients who have an erythroid response, defined as below:

- For non-transfusion dependent (NTD) patients, a hemoglobin increase of ≥ 1.5 g/dL from baseline sustained for ≥ 14 days (in the absence of RBC transfusions). Hemoglobin measurements within 14 days following RBC transfusion or after 56 days of last dose will be excluded from analysis.
- For transfusion dependent (TD) patients, a $\geq 20\%$ reduction in RBC transfusion burden during any rolling 12-week window on treatment compared to baseline. The rolling 12-week window starts on Day 1 and increments by 1 day, e.g., from day 1 to day 84, day 2 to day 85, day 3 to day 86, etc. The search window ends on last dose day + 56 days or last day of hemoglobin measurement, whichever is earlier.

A point estimate of the proportion of patients having a response will be presented along with its associated exact 95% confidence interval based on binomial distribution for NTD and TD patients separately.

The complete hemoglobin measurements and RBC transfusion records will be listed for each patient.

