5.7.2. Secondary Efficacy Endpoints

5.7.2.1. Modified Erythroid Response

Modified erythroid response rates will be defined as below for NTD and TD patients.

For non-transfusion dependent (NTD) patients:

- The proportion of patients with a mean increase of ≥ 1.0 g/dL from pretreatment hemoglobin during any rolling 8 weeks.
- The proportion of patients with a mean increase of ≥ 1.5 g/dL from pretreatment hemoglobin during any rolling 8 weeks.
- The proportion of patients with a mean increase of ≥ 1.0 g/dL from pretreatment hemoglobin during any rolling 12 weeks
- The proportion of patients with a mean increase of ≥ 1.5 g/dL from pretreatment hemoglobin during any rolling 12 weeks

For transfusion dependent (TD) patients:

- The proportion of patients who have $\geq 50\%$ reduction in RBC transfusion burden compared to pretreatment using 12-week intervals.
- The proportion of patients who have $\geq 50\%$ reduction in RBC transfusion burden compared to pretreatment using 8-week intervals.
- The proportion of patients who have no RBC transfusions ≥ 8 weeks.

For each of the above defined modified erythroid response rate, a point estimate will be presented along with the exact 95% confidence interval based on binomial distribution.

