5.7.2.2. Time to and Duration of Erythroid Response

Time to and duration of erythroid response will be analyzed for erythroid responders defined as below:

- For NTD patients, mean increase of ≥ 1.0 g/dL from pretreatment hemoglobin during any rolling 12 weeks
- For TD patients, $\geq 50\%$ reduction in RBC transfusion burden compared to pretreatment using 12-week intervals.

Time to erythroid response will be defined as the time from the first dose date to the first date of any rolling 12-week window achieving above erythroid response.

Duration of erythroid response will be defined as the time from the starting date of the first rolling 12-week window achieving response to the last date of the consecutive rolling 12-week window achieving response. When there are multiple disjoint intervals with response, the longest interval will be used. Patients with response ongoing by the analysis cutoff day will be censored.

Both time to and duration of erythroid response will be analyzed as continuous variables and summarized by descriptive statistics. In addition, duration of erythroid response will also be analyzed as a time to event endpoint.

The derivations of time to and duration of erythroid response will be listed for each patient.

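### The SAP 5.7 efficacy cut-off turns on an undefined transfusion-record date; programmed as worded, it drops the final transfusion-free period from the secondary endpoints

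*SAP*

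**What the plan says.** SAP 5.7 sets general rules for deriving efficacy endpoints: "In general, below rules apply to the derivations of efficacy endpoints which utilize hemoglobin and RBC transfusion data unless specified otherwise". One of these rules gives each patient an analysis cut-off day, "defined as the last dose + 56 days or the last date from transfusion record data, whichever is earlier". The definitions in SAP 5.1 do not cover the second date, and nothing else in either document does.

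The endpoints stand as follows against that rule.

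- **TD primary (SAP 5.7.1)** has its own end date: "The search window ends on last dose day + 56 days or last day of hemoglobin measurement, whichever is earlier".
- **NTD primary (SAP 5.7.1)** restates only the limit of 56 days after the last dose.
- **Secondary response endpoints (SAP 5.7.2.1)** state no end date, so the general rule governs them. For TD patients they are a reduction of at least 50% over 12 weeks, the same over 8 weeks, and "The proportion of patients who have no RBC transfusions" for at least 8 weeks. For NTD patients they are rolling 8- and 12-week mean hemoglobin increases.
- **Time to and duration of response (SAP 5.7.2.2)** use rolling 12-week windows and refer back to the cut-off: "Patients with response ongoing by the analysis cutoff day will be censored".

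Protocol 15.2.2 counts any 12-week interval after Cycle 1 Day 1 within treatment plus follow-up. SAP 5.13 lists no change to that.

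**The concern.** Elsewhere the SAP uses the term transfusion records for the transfusions themselves. SAP 5.6.2 says: "The complete RBC transfusion records prior to and during treatment will be listed for each patient". A programmer who takes the latest date in that dataset gets the date of the last transfusion. I call this the literal reading.

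On that reading the end of the window depends on the outcome. Time without transfusion counts only if a later transfusion closes it, so a patient who stops needing blood can do worse than one who is transfused again. Such a patient still counts in the denominator, because SAP 4.1 says of the ITT population: "This population will be used for all efficacy analysis". Response rates would then be understated.

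Two named secondary objectives rest on these endpoints: the proportion with at least a 50% reduction, and time to and duration of response. Two competent programmers could report different results from the same data.

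**Working it through.** **Inputs**

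- Last possible dose: Day 85 (± 2 days) (SAP Section 9, footnote 14).
- First limb of the cut-off: 85 + 56 = Day 141, which matches the End of Study day in the schedule.
- Rolling windows start on Day 1 and move by one day, the first being Days 1–84 (SAP 5.7.1).
- Assumed for illustration: 2 units per transfusion and a baseline of 8 units per 12 weeks, scaled to 8 × 56/84 = 5.33 units per 8 weeks. A 50% reduction then means at most 4 units in 12 weeks or 2.67 units in 8 weeks.

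**Number of complete windows** = max(0, cut-off day − window length + 1)

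| Cut-off day | 12-week (84 days) | 8-week (56 days) |
|---|---|---|
| 141 | 58 | 86 |
| 120 | 37 | 65 |
| 99 | 16 | 44 |
| 84 | 1 | 29 |
| 83 | 0 | 28 |
| 56 | 0 | 1 |
| 55 | 0 | 0 |
| 36 | 0 | 0 |

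On the literal reading, a patient last transfused before Day 84 has no 12-week window, and one last transfused before Day 56 has no 8-week window either.

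**Patient A, transfused on Days 15 and 36 only**

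- Cut-off Day 141: no 12-week window holds more than 4 units, so 58 of 58 qualify. The 8-week windows starting on Days 1–15 hold both transfusions (4 units) and fail, so 86 − 15 = 71 of 86 qualify. The longest transfusion-free run is Days 37–141, which is 105 days. All three TD secondary response endpoints are met.
- Literal cut-off Day 36: no complete window of either length. The longest run is Days 16–35, which is 20 days. All three are failed.
- The TD primary for the same patient, if hemoglobin is measured on Day 141, still has 58 windows. Days 1–84 alone give 1 − 4/8 = 50%, above the 20% required.

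**Patient B, as A but transfused again on Day 120**

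- Literal cut-off Day 120: no 12-week window holds all three transfusions, because that needs a start by Day 15 and an end on Day 120 or later (start on Day 37 or later). So 37 of 37 qualify. Of the 8-week windows, 65 − 15 = 50 of 65 qualify. The longest run is Days 37–119, which is 83 days. All three are met.

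The extra transfusion turns three failures into three successes.

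**Patient C, transfused on Days 15, 57 and 99**

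- No 84-day window holds all three transfusions (start by Day 15 against start on Day 16 or later), so every window qualifies under either cut-off.
- Cut-off Day 141: 58 of 58, duration Days 1–141 = 141 days. Literal cut-off Day 99: 16 of 16, duration Days 1–99 = 99 days.
- Response is ongoing at both cut-offs, so both values are censored in the time-to-event analysis. Only the descriptive summary treats 99 days as the duration.

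**A patient with no on-study transfusion.** The latest transfusion record is before Day 1 or does not exist, so no on-study window can be formed. This also removes the rolling hemoglobin means for such an NTD patient.

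**The case against.** The best case on the other side is that the literal reading cannot have been meant. The rule applies to each patient and to NTD hemoglobin means, and a last-transfusion date would leave many of those patients without a window. A date taken from record data, used to set an analysis cut-off, also reads naturally as a statement of how far the data run. SAP 3.3 gives a reason for such a limit. It says of patients who go straight into the extension study: "These patients may forego the End of Study (EOS) visit in study A536-04 to begin study A536-06". A patient last assessed on Day 113 would properly have 113 − 84 + 1 = 30 windows of 12 weeks and not 58. On this reading the limb does its job and no ascertained time is lost. This argument stands, and it makes the point an ambiguity and not a demonstrated error.

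A reader might also infer more than the documents support:

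- **That the TD primary contradicts the general rule or is damaged by it.** It does not contradict it: the rules in 5.7 yield where an endpoint specifies otherwise, and 5.7.1 does so. The TD primary does not use the disputed date. That no reason is given for the different end date is an observation, not a fault.
- **That the rule flatters the drug.** The loss falls on patients who stop needing transfusion, so it runs the other way.
- **That observed durations become shorter throughout.** In the time-to-event analysis the effect is earlier censoring; only the descriptive summary falls.
- **That patients are followed for less time.** The rule ends the derivation window, not follow-up.

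It is also fair that these analyses are descriptive, and that transfusion records and duration derivations are listed by patient, so a misreading could be found and corrected.

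**Conclusion.** The point holds as an undefined operative term. Followed as worded, it makes the window end on the outcome and narrows the protocol's definition of an on-study interval without being listed as a change. The endpoints exposed are the three TD secondary response endpoints, time to and duration of response, and the NTD rolling means in patients with no on-study transfusion.

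The consequence for an individual can be complete: all three TD endpoints failed despite 105 transfusion-free days, or a descriptive duration of 99 days in place of 141. These examples assume a last dose on Day 85, data to Day 141 and, where units matter, 2 units per transfusion against a baseline of 8 units per 12 weeks. The window counts and transfusion-free runs do not depend on the unit assumptions.

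The documents give no on-study transfusion pattern, so neither the number of patients affected nor the change in any response rate can be derived. If the phrase means the date through which transfusion status was ascertained, the effect is nil and only the wording needs attention.

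**What to change.** In SAP 5.7, replace the second limb of the cut-off with: *the last on-study date through which RBC transfusion status was ascertained (study exit or rollover, if earlier)*. Add that the date of a transfusion alone never ends the window. For the NTD hemoglobin endpoints, state that the limit is last dose + 56 days or study exit.

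If ascertainment was always the meaning, a defining sentence is enough for the transfusion endpoints. Using the same end date for the TD primary would be tidier but is optional.

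The cost is one or two sentences and the matching derivation code. No new data are needed.

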5.7.1. Primary Efficacy Endpoint

The primary efficacy endpoint is the proportion of β -thalassemia patients who have an erythroid response, defined as below:

- For non-transfusion dependent (NTD) patients, a hemoglobin increase of ≥ 1.5 g/dL from baseline sustained for ≥ 14 days (in the absence of RBC transfusions). Hemoglobin measurements within 14 days following RBC transfusion or after 56 days of last dose will be excluded from analysis.
- For transfusion dependent (TD) patients, a $\geq 20\%$ reduction in RBC transfusion burden during any rolling 12-week window on treatment compared to baseline. The rolling 12-week window starts on Day 1 and increments by 1 day, e.g., from day 1 to day 84, day 2 to day 85, day 3 to day 86, etc. The search window ends on last dose day + 56 days or last day of hemoglobin measurement, whichever is earlier.

A point estimate of the proportion of patients having a response will be presented along with its associated exact 95% confidence interval based on binomial distribution for NTD and TD patients separately.

The complete hemoglobin measurements and RBC transfusion records will be listed for each patient.

5.7.2. Secondary Efficacy Endpoints

5.7.2.1. Modified Erythroid Response

Modified erythroid response rates will be defined as below for NTD and TD patients.

For non-transfusion dependent (NTD) patients:

- The proportion of patients with a mean increase of ≥ 1.0 g/dL from pretreatment hemoglobin during any rolling 8 weeks.
- The proportion of patients with a mean increase of ≥ 1.5 g/dL from pretreatment hemoglobin during any rolling 8 weeks.
- The proportion of patients with a mean increase of ≥ 1.0 g/dL from pretreatment hemoglobin during any rolling 12 weeks
- The proportion of patients with a mean increase of ≥ 1.5 g/dL from pretreatment hemoglobin during any rolling 12 weeks

For transfusion dependent (TD) patients:

- The proportion of patients who have $\geq 50\%$ reduction in RBC transfusion burden compared to pretreatment using 12-week intervals.
- The proportion of patients who have $\geq 50\%$ reduction in RBC transfusion burden compared to pretreatment using 8-week intervals.
- The proportion of patients who have no RBC transfusions ≥ 8 weeks.

For each of the above defined modified erythroid response rate, a point estimate will be presented along with the exact 95% confidence interval based on binomial distribution.

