10.2.2. RBC Transfusions

Concurrent treatment for anemia with blood transfusions is allowed at the discretion of the investigator, for low hemoglobin levels, symptoms associated with anemia (e.g., hemodynamic or pulmonary compromise requiring treatment) or a comorbidity.

For any RBC transfusions received during the study, collect hemoglobin values just prior to transfusion.

Each TD patient in the expansion cohort will have a defined “pre-transfusion hemoglobin threshold” which will be calculated based on transfusion history and will be used for determining when to transfuse during the study. The baseline pre-transfusion hemoglobin threshold will be the mean of all documented pre-transfusion hemoglobin values during the 12 weeks prior to

C1D1. During treatment, if the pre-transfusion hemoglobin value is increased by ≥ 1 g/dL compared to the baseline pre-transfusion hemoglobin threshold for that patient, transfusion should be delayed by a minimum of 7 days and/or the number of units transfused should be reduced by 1 or more RBC units. Patients may be transfused at the investigator's discretion for symptoms related to anemia or other requirements (e.g., infection).

For the first dose of ACE-536, dosing should occur after a minimum of 7 days post-transfusion; subsequent doses should not be given within 24 hours of transfusion or planned transfusion.

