5. STATISTICAL METHODOLOGY

5.1. Definitions

Transfusion Dependent (TD)

Based on protocol, TD patients are defined as those who required ≥ 4 units of RBCs every 8 weeks (confirmed over 6 months prior to Cycle 1 Day 1).

For programming implementation, a patient is defined as TD if the total RBCs is ≥ 11 units during 26 weeks on or prior to Cycle 1 Day 1.

Non-Transfusion dependent (NTD)

NTD patients are those who do not meet the above definition for TD. For programming implementation, NTD patients are defined as those who received < 11 units of RBCs during 26 weeks on or prior to Cycle 1 Day 1.

Baseline Hemoglobin

Baseline hemoglobin will be an average of hemoglobin measurements within 28 days of Cycle 1 Day 1, excluding measurements within 14 days following RBC transfusion.

Baseline Transfusion Burden

Baseline transfusion burden will be calculated as the total amount of RBC transfusions during the 12 weeks on or prior to Cycle 1 day 1.

Baseline for Other Parameters

Baseline erythropoietin (EPO) is defined as the maximum test value within 28 days of Cycle 1 Day 1. For all other parameters, baseline is defined as the last observation on or prior to Cycle 1 Day 1.

Transfusion Unit Conversion

The transfusion amount measured in unit “mL” will be converted to “units” according to medical review.

End of Treatment (EOT)

Procedures and evaluations for the end of treatment visit should be performed 28 days (± 7 days) after the last dose of ACE-536.

End of Study (EOS)

Procedures and evaluations for the end of study visit should be performed 28 days (± 7 days) after the Day 113/EOT visit (56 days after the last dose of ACE-536).

Combined Dose Groups

Low dose group includes patients on 0.2mg/kg and 0.4 mg/kg dose cohorts. High dose group include patients with dose level 0.6 mg/kg and above. Suitable summaries may be presented by low/high dose as specified.

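### The modified NTD hemoglobin responses do not require absence of RBC transfusions, so carry-over beyond 14 days can count toward a secondary response

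*SAP*

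**What the plan says.** SAP 5.7.1 places two conditions on the NTD primary response. The rise must be sustained "in the absence of RBC transfusions", and, as a separate sentence, "Hemoglobin measurements within 14 days following RBC transfusion or after 56 days of last dose will be excluded from analysis".

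SAP 5.7.2.1 defines four modified NTD responses: a mean rise of at least 1.0 or 1.5 g/dL "from pretreatment hemoglobin during any rolling 8 weeks", and the same two thresholds over 12 weeks. SAP 5.7.2.2 takes one of these, a mean rise of at least 1.0 g/dL "from pretreatment hemoglobin during any rolling 12 weeks", as the NTD responder definition for time to and duration of response. None of these definitions mentions transfusion.

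The general rules in SAP 5.7 do reach them: "In general, below rules apply to the derivations of efficacy endpoints which utilize hemoglobin and RBC transfusion data unless specified otherwise". One of those rules is "Hemoglobin measurements within 14 days following RBC transfusion will be excluded from efficacy analysis". Sections 5.7.2.1 and 5.7.2.2 specify nothing different.

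NTD patients can be transfused on study. SAP 5.1 classes a patient as NTD on fewer than 11 "units of RBCs during 26 weeks on or prior to Cycle 1 Day 1", and Protocol 10.2.2 states: "Concurrent treatment for anemia with blood transfusions is allowed at the discretion of the investigator".

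**The concern.** Values from day 15 after a transfusion enter the rolling mean. If transfused cells still raise hemoglobin then, an NTD patient who was transfused on study can be scored as a secondary responder and given a time to and duration of response, although the drug did nothing. Time to and duration of response is a stated secondary objective. The trial has no control arm, so the summary rate alone would not show that transfusion had contributed. The SAP also sets no minimum number of hemoglobin values per window, so a response can rest on very few values once the exclusion is applied.

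**Working it through.** The plan gives no figure on this point, so there is none to reproduce. The check asks whether transfusion carry-over alone can satisfy the definitions as written.

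**Inputs from the documents.** Hemoglobin visits after the first dose fall on Days 8 to 99 weekly, then Days 113 and 141 (schedule of events). Values 1 to 14 days after a transfusion are removed. Follow-up ends at last dose + 56 days, which is 85 + 56 = Day 141.

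**Assumptions, not in the documents.** A rise of g = 0.7 or 1.0 g/dL per unit, lost linearly over L = 60 or 90 days; one transfusion of U units; no drug effect; hemoglobin otherwise constant at a fixed distance *off* below baseline.

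**Formula.** A value taken *a* days after the transfusion differs from baseline by U × g × (1 − a/L) − off, with the transfusion term zero once a exceeds L. A window qualifies if the mean of its remaining values is at least 1.0 g/dL.

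**Worked case.** 2 units on Day 43, g = 1.0, L = 90, off = 0.
- 8-week window, Days 44 to 99: the values on Days 50 and 57 are removed (a = 7 and 14). Days 64, 71, 78, 85, 92 and 99 remain, with a = 21, 28, 35, 42, 49, 56 and mean 38.5. Mean rise = 2 × (1 − 38.5/90) = 1.14 g/dL. Qualifies.
- 12-week window, Days 44 to 127: Day 113 (a = 70) is added, so mean a = (6 × 38.5 + 70)/7 = 43. Mean rise = 2 × (1 − 43/90) = 1.04 g/dL. Qualifies.
- With untransfused hemoglobin 0.5 g/dL below baseline, the two means are 0.64 and 0.54 g/dL. Neither qualifies.
- With g = 0.7 and L = 60, off = 0, the 8-week mean is 1.4 × (1 − 38.5/60) = 0.50 g/dL. Does not qualify.

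**All transfusion days, best window each time.** Days 9 to 85 give 77 possible days for the 8-week criterion; Days 9 to 57 give 49 for the 12-week criterion. The entries are shares of possible transfusion days, not of patients.

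| Units; g; L | Untransfused Hb | 8-week mean ≥ 1.0 | 12-week mean ≥ 1.0 |
|---|---|---|---|
| 2; 1.0; 90 | at baseline | 77/77 (100%) | 25/49 (51%) |
| 2; 1.0; 90 | 0.5 below | 1/77 (1%) | 0/49 |
| 2; 1.0; 90 | 1.0 below | 0/77 | 0/49 |
| 3; 1.0; 90 | 0.5 below | 77/77 (100%) | 25/49 (51%) |
| 3; 1.0; 90 | 1.0 below | 18/77 (23%) | 0/49 |
| 2; 0.7; 60 | at baseline | 0/77 | 0/49 |
| 3; 0.7; 60 | at baseline | 24/77 (31%) | 0/49 |
| 3; 0.7; 60 | 0.5 below | 0/77 | 0/49 |

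**Sparse windows.** In the first row, requiring at least 4 values per window still leaves 90% and 51%, so few values are not the main cause. They do matter at the edge: a 2-unit transfusion on Day 84 gives its best 8-week mean from Days 99 and 113 only, (1.667 + 1.356)/2 = 1.51 g/dL.

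**Would a transfusion-free window suffice?** No. The windows in the worked case start on Day 44, the day after the transfusion, so they are already transfusion-free. Adding that condition leaves every count in the table unchanged. Also disallowing a transfusion in the 8 weeks before the window takes the first row to 0/77 and 0/49.

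**The case against.** The strongest reply is that a transfusion rule already governs these endpoints. The 14-day exclusion is the only operational rule written beside the primary's clause, and it is also the rule used for baseline. It keeps the post-transfusion peak out of the mean, and any harm needs carry-over after day 14, whose size and duration the documents do not give. That stands as a limit on size. It does not close the gap: SAP 5.7.1 states both the absence of transfusion and the 14-day exclusion, and the modified responses inherit only the second.

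A second reply is that patients are transfused when hemoglobin is low, so holding untransfused hemoglobin at baseline is generous. This also stands. It removes nearly all of the 2-unit effect, though not the 3-unit effect at 1.0 g/dL per unit and 90 days.

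A third is that nothing is tested on these endpoints, and that hemoglobin values, transfusion records and each patient's time-to and duration derivation are listed, so a transfused responder can be found. True, but a reader of the rates would have to go looking.

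Three stronger readings are tempting and not supported:
- *The SAP removed the clause from these endpoints.* The protocol's own 8-week NTD endpoints (15.2.3) never carried it. The contrast is with the primary only.
- *The bias always favours the drug.* An on-study transfusion can only raise the post-baseline mean. But baseline uses the same 14-day exclusion, and protocol eligibility permits an NTD patient up to 3 units in the 8 weeks before Cycle 1 Day 1. Carry-over into baseline would make a response harder to reach.
- *A transfusion will by itself produce a response.* That depends on inputs that the documents do not supply.

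**Conclusion.** The concern holds in a limited form. The modified NTD responses and the NTD time-to and duration responder definition lack the primary's condition, and the 14-day exclusion is their only protection. Whether this matters depends on carry-over beyond 14 days, on units given, and on how far untransfused hemoglobin lies below baseline. Over the assumed range the result runs from no effect to a qualifying 8-week window on every possible transfusion day. The documents do not say how many NTD patients were transfused on study, so no effect on the reported rates can be computed. The point is a worthwhile, inexpensive improvement to descriptive secondary endpoints. It changes neither the primary endpoint nor the sample size.

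**What to change.** In SAP 5.7.2.1 and 5.7.2.2, keep the current NTD rates and the time-to and duration summary. Beside them, report a version in which a window counts only if no RBC transfusion was given on study in the window or in a pre-specified carry-over period before it, for example 8 weeks. Flag every responder who was transfused on study.

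The cost is one sentence in the SAP and one programming condition; the transfusion records are already collected and listed.

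The downside should be stated. With Day 141 as the last day, 12-week windows can start on Days 1 to 58 (141 − 84 + 1 = 58) and 8-week windows on Days 1 to 86 (141 − 56 + 1 = 86). With an 8-week carry-over:
- 12-week criterion: the Day 1 window is lost to any transfusion up to Day 84, and the Day 58 window to any from Day 58 − 56 = 2. A transfusion on Days 2 to 84 therefore makes the patient a non-responder.
- 8-week criterion: the Day 1 window is lost up to Day 56, and the Day 86 window from Day 86 − 56 = 30. A transfusion on Days 30 to 56 has the same result.

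The rate among transfused NTD patients will therefore fall, which is why this version belongs beside the current one and not in its place. The length of the carry-over period is the sponsor's choice, to be fixed and justified in advance.
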